11.1.4 Study outcomes

Primary outcome

Composite of recurrent AIS, sICH, systemic embolism and/or death within 90 days after randomisation

Secondary outcomes are:

- a) Functional outcomes defined as a shift (improvement) in scores on the mRS at 90 days
- b) Any ICH reported by investigators or after central adjudication of relevant brain imaging within 90 days after randomisation
- c) sICH, in which ICH is associated with substantial neurological deterioration or death according to various definitions within 90 days
- d) Death or disability by scores 3-6 on the mRS at 3 months
- e) Separately on death and disability at 3 months
- f) Length of hospital stay
- g) HRQoL by the EuroQoL at 3 months

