6.8. Study Outcomes

Primary outcome

Functional outcomes defined as a shift (improvement) in scores on the mRS at 90 days (3 months). The mRS is a widely used instrument for grading the impact of stroke treatments, with scaling of: 0 = no symptoms at all; 1 = no significant disability despite symptoms, but able to carry out all usual duties and activities; 2 = slight disability, unable to carry out all

previous activities but able to look after own affairs without assistance; 3 = moderate disability requiring some help, but able to walk without assistance; 4 = moderate-severe disability, unable to walk without assistance and unable to attend to own bodily needs without assistance; 5 = severe disability, bedridden incontinent, and requiring constant nursing care and attention; 6 = dead.

Secondary outcomes are:

- 1) ICH: a) sICH, based on National Institutes of Neurological Diseases and Stroke (NINDS) criteria of brain imaging (or necropsy) confirmed ICH with ≥ 1 points deterioration in NIHSS score or death within 36 hours from baseline; b) sICH, defined by Safe Implementation of Thrombolysis in Stroke-Monitoring Study (SITS-MOST) criteria, as large ('type II') parenchymal ICH with ≥ 4 points decline in NIHSS score or death within 36 hours from baseline; c) sICH, defined by the new Heidelberg Bleeding Classification (HBC) criteria; d) ICH of any type in brain imaging ≤ 7 days of treatment; e) any symptomatic ICH (sICH) after MT within 90 days. ICH will be assessed by CT imaging and adjudicated centrally.³³
- 2) Imaging endpoints: a) infarct size growth assessed by MRI at 48 hours; b) edema volume assessed by CT at Day 7.
- 3) Death or dependency measured by NIHSS at 7 days;
- 4) The followings at 90 days: Death or major disability (mRS 3-6); separately on death and disability (mRS 3-5); health-related quality of life (HRQoL) using EQ-5D; duration of hospitalisation; residence and hospital service cost.

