6.10.5 Follow up Data

Day 1 (Form C)

The primary goal of assessments within the first 24 hours will be to ensure adherence to the allocated the protocol. BP and administered medication will be recorded. BP will be recorded supine in the non-paretic arm from the automated, electronic device used at the Clinical Centre. BP will be recorded every 15 minutes for the first hour, then hourly for the next 5 hours, and 6 hourly from 6 hours to 24 hours. When i.v. boluses are given, HR and BP should be re-checked and recorded 5 and 15 minutes later. The following information will be recorded.

- BP
- BP lowering medication
- GCS and NIHSS scores at 24 hours
- Follow up brain imaging (CT brain and/or MRI) should be undertaken at 24-48 hours post-MT
- If other imaging investigations are performed (i.e. transcranial Doppler), these should be documented in the CRFs
- Antithrombotic medications
- Follow up blood tests
- Standard stroke care assessment

Day 7 or discharge if earlier (Form D)

On Day 7 or on the day of hospital discharge/transfer or death if prior to Day 7, the contact details of the patient or caregiver should be confirmed to facilitate follow up assessments. The following information will be recorded:

- GCS and NIHSS score
- Dependency assessed with the mRS
- BP
- BP lowering medication (medications used during Days 2 to 7)
- Medications and key specific treatment received during hospitalization
- Other aspects of acute stroke management during hospitalization

- Prognosis prediction from clinicians
- Date of discharge or transfer from hospital
- Repeat brain CT or MRI
- Healthcare costs and details of blood pressure lowering treatment.

BP Monitoring Chart (Form E)

As usual nursing care during the study period, the BP assessments in 7 days will be used to check adherence to BP management protocol.

Day 90 Follow-up (Form F)

These assessments are to be undertaken by an investigator who was not involved in the clinical management of the patient, and blind to the randomised treatment allocation. On 90±7 days, all surviving patients will be evaluated through a telephone interview or at a face-to-face consultation.

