Detailed resource utilization data, hospital billing data, physical function and patient reported quality of life data were collected for patients from the time of randomisation through 90-day follow-up. These data were used to calculate direct healthcare costs and QALY during the initial 90-day period based on international and national guidelines.^{34, 35}

- BP
- Dependency assessed with the mRS³⁶
- HRQoL measured by the EQ-5D³⁷
- Patient living status (e.g. home, high care)
- Any complications or hospitalization since going home
- Any medication currently used
- Healthcare related cost.

Death

Patients who have died prior to any of the above scheduled assessments, cause of death documentation will be collected with date and time of death. Copies of post-mortem reports, hospital record entry or death certificate, should be kept with the Patient Contact Details log to assist in trial monitoring by the CCC. An SAE form is to be completed for all deaths during the study period, stating the primary and underlying cause of death.

Withdrawal of allocated management and protocol violations

A form will be provided to record the date and circumstances surrounding any deviation from the protocol or missed assessments.

Consent

Consent will be documented in the patient's progress notes and CRF and the type(s) of consent obtained will also be recorded on the database.

Serious Adverse Events (SAEs)

All SAEs will be recorded on the SAE form, and completed on the electronic CRF or faxed/mailed from a printed form to the CCC within the prescribed time. Additional information may be requested to provide supplementary information on the event and outcome.

Table 2 Schedule of evaluations

Evaluation	Baseline (Prior Randomisation)	Day			365 ^b
		1	7 ^a	90 ^b	
Eligibility	X				
Brain imaging (CT ± angiogram or MRI± angiogram or DSA)	X	X	X		
BP	X (BP x 2)	X** q 15 min 1h 6h	X q12h	X	
HR	X				
ECG	X				
Consent	X				
Medical history, prior medications	X				
Details of rt-PA (if performed) and MT	X				
Physical exam GCS/ NIHSS	X	X	X		
Functional assessment with mRS	X		X	X	
HRQoL assessment with EQ-5D				X	
Routine blood tests	X	X			
BP lowering treatment		X	X	X	
Antithrombotic and other medications		X	X	X	
Standard stroke care		X	X		
Hospitalized or not			X	X	
Contact details for Follow-up		X	X		
Hospital service cost			X	X	
SAEs	X ^c	X	X	X	X

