Early treatment will be started at Day 4 ± 2 of stroke onset.

Late initiation of oral anticoagulation therapy

Late treatment will be started as per current recommendations at Day 12 ± 2 of stroke onset.

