## **3.9 Analysis of substudies**

The main purpose of the substudies is to define recruitment, safety and adherence to the protocol, to inform the feasibility of future confirmatory studies.

Description of the baseline characteristics will be presented by treatment group. Discrete variables will be summarised by frequencies and percentages. Percentages will be calculated according to the number of patients for whom data are available. Continuous variables will be summarised using mean and SD, and median and IQR. Baseline measures will include all socio-demographic, clinical and medical information, collected at baseline.

The main outcomes will be recurrent ischaemic stroke, ICH, death, and any SAE over 12 months. These data will be reported as the number and proportion of subjects experiencing an event. The effect of the intervention will be estimated using the same approach as in the binary analysis of mRS (see Section 3.8.1). We will apply the covariate adjustments described in Section 3.7.2; however, no subgroup or imputed analysis will be performed on this outcome.

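### Anticoagulation substudy: if the Day 7 scan is routine, silent ICH after the start of anticoagulation is looked for routinely only in the early arm, so the any-ICH contrast is biased against early treatment

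*Protocol*

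**What the plan says.** Protocol 11.1.3 sets the two arms: "Early treatment will be started at Day 4 ± 2 of stroke onset" and "Late treatment will be started as per current recommendations at Day 12 ± 2 of stroke onset". Protocol 11.1.4, secondary outcome b, is "Any ICH reported by investigators or after central adjudication of relevant brain imaging within 90 days after randomisation". Symptomatic ICH is a separate outcome (c), so b includes silent bleeds.

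Table 2 in Protocol 6.10.5 marks brain imaging at baseline, Day 1 and Day 7 (or discharge if sooner), with no mark at Day 90 or Day 365. Form D lists "Repeat brain CT or MRI" at the same visit. The substudy's own data collection (11.1.6) adds adherence and no scan.

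Two other places describe imaging differently. Protocol 6.10 gives a baseline scan, one at 24-48 hours, and later scans for deterioration or another clinical reason. Appendix 3 gives a follow-up scan at 24 hours plus scans for deterioration or suspected ICH. Neither names a routine Day 7 scan.

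SAP 3.9, which covers both substudies, says: "The main outcomes will be recurrent ischaemic stroke, ICH, death, and any SAE over 12 months". It estimates the treatment effect with the binary logistic model used for the mRS. It does not say which ICH definition it means.

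**The concern.** An outcome that counts silent bleeds depends on when patients are scanned. Here the arms differ in when treatment starts, while the scan calendar is the same for both. If the last routine scan falls between the two start windows, it shows the early arm on treatment and the late arm before treatment. A silent bleed that follows a late start would be found only if something else prompted a scan.

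The main trial does not have this problem: Protocol 6.8 limits ICH of any type to 7 days and carries only symptomatic ICH to 90 days. The substudy carries any ICH to 90 days without a later scan.

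The substudy aims to weigh recurrence against bleeding (11.1.1), and SAP 3.9 gives safety as one of the things it should establish for a confirmatory study. A contrast shaped by scan timing could make early treatment look worse than it is, or conceal an excess of bleeding in the late arm.

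**Working it through.** The plan gives no rate for any ICH, so it has no figure of its own to reproduce on this point. The substudy's one sample size, 2418 for the composite (11.1.5), does reproduce at an assumed two-sided 5%: (1.960 + 1.2816)² × (0.20 × 0.80 + 0.15 × 0.85) / 0.05² rounds up to 1209 per arm. Nothing below depends on it.

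**Step 1: dates.** Assume 0 to 1.3 days from onset to randomisation. A Day 7 scan then falls at 7.0 to 8.3 days from onset.
- Early start, Day 2-6: the scan comes 7.0 − 6 = 1.0 to 8.3 − 2 = 6.3 days after it.
- Late start, Day 10-14: the scan comes 10 − 8.3 = 1.7 to 14 − 7.0 = 7.0 days before it.
- The 24-48 hour scan comes before the early start or at the earliest edge of its window, so it is close to neutral.
- A discharge scan before Day 7 can precede an early start on Day 5 or 6. That weakens the asymmetry but cannot reverse it, because no scheduled scan follows a late start.

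**Step 2: model.** All rates are assumptions.
- q = background ICH seen on early scans, equal in both arms: 20-40%
- d = further silent ICH after the start of anticoagulation, equal in both arms: 3-8%
- h = share of the early arm's silent ICH visible by Day 7: 50-100%
- f = share of the remaining silent ICH found on triggered scans: 10-30%

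Observed early = q + (1 − q) × d × [h + (1 − h) × f]

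Observed late = q + (1 − q) × d × f

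Difference = (1 − q) × d × h × (1 − f)

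**Step 3: extremes, with no true difference between arms.**

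| q | d | f | h | Early | Late | Difference (points) | OR |
|---|---|---|---|---|---|---|---|
| 0.40 | 0.03 | 0.30 | 0.5 | 41.17% | 40.54% | 0.63 | 1.03 |
| 0.40 | 0.03 | 0.30 | 1.0 | 41.80% | 40.54% | 1.26 | 1.05 |
| 0.20 | 0.08 | 0.10 | 0.5 | 23.52% | 20.64% | 2.88 | 1.18 |
| 0.20 | 0.08 | 0.10 | 1.0 | 26.40% | 20.64% | 5.76 | 1.38 |

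The last OR, for example, is (0.264/0.736) / (0.2064/0.7936) = 1.38.

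**Step 4: a real late-arm excess.** Take q = 0.30, d = 3% early and 6% late. The true totals are 0.30 + 0.70 × 0.03 = 32.1% early and 0.30 + 0.70 × 0.06 = 34.2% late. With f from 0.1 to 0.3 the late arm shows 30.4-31.3%. The early arm shows 32.1% if h = 1 and 31.2-31.4% if h = 0.5. The late arm's excess disappears or changes sign.

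**Step 5: no routine Day 7 scan.** Set h = 0. Both arms then depend on triggered scans, and the difference is 0.

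**The case against.** The strongest objection is that the bias needs a routine Day 7 scan, and the documents disagree on whether there is one. If Protocol 6.10 and Appendix 3 govern, routine imaging ends at about the earliest possible early start. Triggered scans are open to both arms through Day 90, so the bias largely goes. This stands, and it makes the point conditional. On the other side, Table 2, Form D and the Day 7 CT oedema outcome in 6.8 all point to a later scan. The SAP's wider oedema window of days 2-7 does not settle the matter.

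A second objection is that much of the remedy is already present. Symptomatic ICH to 90 days is in the substudy's primary composite and in outcome c. Of the symptomatic definitions in 6.8, Heidelberg and definition e carry no 36-hour limit. This also stands: those outcomes are much less affected, because a symptomatic bleed prompts a scan in either arm.

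Three stronger readings are tempting, and the documents do not support them.
- A reader might infer that silent bleeds count against early treatment only. They do not: haemorrhagic transformation seen on the early scans counts in both arms. Only bleeding after the start of anticoagulation is looked for unequally.
- A reader might infer that SAP 3.9 makes any ICH, as opposed to symptomatic ICH, a main outcome. The term there is undefined, and SAP 3.8.2 makes Heidelberg the primary measure among five definitions.
- A reader might take the size from full detection in the early arm, 1.3 to 5.8 points. A scan a few days after the start will miss some of that arm's bleeds too. If half show by Day 7, the excess halves to 0.6-2.9 points.

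**Conclusion.** The concern holds on condition that the Day 7 or discharge scan is routine. The last scheduled scan then usually falls after the early start and always before the late start. The any-ICH contrast to 90 days is biased against early treatment, as is the SAP 3.9 ICH contrast if it means any ICH. Under the assumed rates the spurious excess is about 0.6 to 5.8 percentage points (OR about 1.03 to 1.38). The direction is the same throughout the range, but the size rests wholly on assumptions.

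The reach is limited. This is a secondary outcome of a pilot, and the composite that drives the substudy's sample size uses symptomatic ICH. It still merits correction, because as written the plan can yield a bleeding estimate that reflects the scan calendar.

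**What to change.** 1. Reconcile Protocol 6.10 and Appendix 3 with Table 2 and Form D, so that it is clear whether a Day 7 or discharge scan is routine.
2. In SAP 3.9, state that the ICH outcome compared between early and late anticoagulation is symptomatic ICH to day 90, using Protocol 6.8 item "e) any symptomatic ICH (sICH) after MT within 90 days". Do not use the NINDS or SITS-MOST definitions, whose 36-hour limit usually passes before anticoagulation begins.
3. Report any ICH (11.1.4 b) descriptively, split by scheduled versus clinically indicated scan and by before versus after the patient's own anticoagulation start. State that the scheduled-scan part compares early-treated with not-yet-treated patients.

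The cost is wording in the SAP and protocol. No new scans are needed, though the split requires each patient's actual start date and the reason for each scan. The downside is fewer bleeding events in the pilot's formal comparison.

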11.1.5 Sample size

In this and the other substudy, the aim is to recruit as many patients to inform the sample size estimates for the main study. Our preliminary sample size calculation to provide a reliable assessment of the treatment effect is outlined below.

The results of Pre-TIMING study in Sweden revealed 12% of primary outcomes (4% of recurrent ischemic stroke, 3% of sICH, and 4% of all-cause mortality) in AF-related AIS patients with OAC therapy at 90 days.⁶² Given more severe patients are being enrolled in ENCHANTED2, the event rate is expected to be around 20%. A sample size of 2418 subjects provides 90% power to detect a 5% absolute (25% relative) risk reduction on a composite outcomes at 90 days between the randomised groups in AIS patients with successful post-MT reperfusion.

11.1.6 Data collection and follow up

Day 90 ($\pm 7d$)

The adherence of the anticoagulation therapy in each randomised group will be collected through 90-day follow-up.

11.2 Duration of dual antiplatelet therapy (DAPT)

11.2.1 Aims

Compared with a standard duration of DAPT (3 months), a short duration (6 weeks) of DAPT is at least as effective ('not inferior') in reducing the risk of recurrent stroke over 12 months, in AIS patients with LAA who undertook MT (i.e. corresponding null hypothesis is that short duration of treatment is inferior than standard duration on this outcome).

11.2.2 Background and rationale

The effectiveness of APT for the secondary prevention of AIS is well recognized,⁶³ but the efficacy and safety of DAPT in MT-LVO patients remains controversial.^{64, 65} Whilst European guidelines do not recommend long-term DAPT in AIS patients, AHA/ASA guidelines (2018) recommend 21-days of DAPT with aspirin and clopidogrel commenced within 24 hours of symptom onset with minor stroke (Class IIa; Level of Evidence B) based on the Clopidogrel in High-Risk Patients With Acute Nondisabling Cerebrovascular Events (CHANCE)⁴¹ and Platelet-Oriented Inhibition in New TIA and Minor Ischemic Stroke (POINT)⁶⁹ trials. In CHANCE, 5170 Chinese minor AIS/high-risk TIA patients were randomly assigned to either DAPT (clopidogrel at an initial dose of 300 mg, followed by 75 mg per day for 90 days, plus aspirin at a dose of 75 mg per day for the first 21 days) or placebo plus aspirin (75 mg per day for 90 days), to show DAPT was superior in reducing the risk of recurrent stroke at 90 days (HR 0.68,

95% CI 0.57-0.81; $P <0.001$), with no significant increase in ICH risk (HR 1.41, 95% CI 0.95-2.10; $P = 0.09$) compared to monotherapy. The multinational POINT trial showed a 28% reduction in stroke recurrence with DAPT compared to aspirin monotherapy, but major bleeding events were double.⁶⁶ A meta-analysis published in 2013 included 14 RCTs of DAPT versus aspirin among 9102 AIS/TIA patients, showed that DAPT significantly reduce the risk of recurrent stroke in 3 months (RR 0.69, 95% CI 0.6-0.8), without increasing the major bleeding events (RR 1.35, 95%CI 0.7-2.59).⁶⁵ However, a recent meta-analysis including POINT further explored the optimal duration of DAPT to show that short-term (one month) reduced the risk of recurrent AIS (RR 0.53; 95% CI 0.37-0.78) without a significant increased the risk of major bleeding (RR 1.82; 95% CI 0.91-3.62).⁶⁷

The application of these findings to LVO/MT patients is limited as they are confined to those with minor AIS (NIHSS < 4) or high-risk TIA as an acute therapy in an unstable plaque. The only trial focussed on the efficacy of DAPT in patients with LAA was Stenting and Aggressive Medical Management for Preventing Recurrent Stroke in Intracranial Stenosis (SAMMPRI), which included patients with recent AIS/TIA attributed to 70-99% stenosis of a major intracranial artery, randomly assigned to aggressive medical management alone (including with a dose of 325 mg aspirin and 75 mg clopidogrel per day for 90 days) or aggressive medical management plus percutaneous transluminal angioplasty and stenting (PTAS) with the use of the Wingspan stent system.⁶⁸ Enrolment was stopped after 451 patients were randomised because the 30-day rate of stroke or death in the PTAS group was significantly higher than medical-management group (14.7 vs. 5.8%, $P =0.002$), indicating aggressive medical management was superior to PTAS alone. Despite the lack of direct evidence, many clinicians prescribe DAPT to those patients with LAA where there is high risk of recurrent stenosis, for example intra-MT endothelial trauma or placement of a stent to maintain reperfusion. The standard duration of DAPT in such cases is 3 months post-MT. A shorter duration of DAPT for LAA patients post-MT may provide greater benefit over ongoing risk of major bleeding.

In summary, the efficacy and safety of DAPT for secondary prevention as well as the optimal duration in patients with major stroke remains unresolved. This imbedded substudy aims to determine the effectiveness of a short duration of DAPT in patients with LAA who receive MT.

11.2.3 Study design

This substudy – **Duration of DAPT** - is a pilot study imbedded in the main ENCHANTED2 study. Consent will be obtained prior to MT procedure, but randomisation will be undertaken post-MT at the same time of the main study, according to separate eligibility criteria. Randomised allocation (1:1 ratio) of intervention will be done via the same randomisation system as the main study, according to minimized method stratified by site and randomisation of BP intervention. The patients will be either allocated to short duration (6 weeks) or standard duration (3 months) of DAPT within 48 hours after AIS onset, and to be maintained on antiplatelet monotherapy (aspirin or clopidogrel) thereafter.

Study population

All patients randomised in the main trial, who have a final diagnosis of LAA-related AIS will be considered for enrolment in this sub-study. *In comparison to all other randomised patients, patients included in this substudy are followed up for 12 months.*

Inclusion and exclusion criteria

To be eligible for inclusion for this substudy, patients who has been enrolled into the main study **ARE** to still satisfy all of the following criteria:

- Final diagnosis of LAA confirmed by imaging during MT procedure

- b) Provision of written informed consent (or via an appropriate proxy, according to local requirements)

Patients will **NOT** be eligible if there is one or more of the following:

- c) Definite contraindication to both aspirin and clopidogrel

Treatment allocation

Short duration of DAPT

The patients will receive oral (including nasogastric if required) DAPT (aspirin 100 mg and clopidogrel 75 mg per day) for **6 weeks** within 48 hours after stroke onset if no PH confirmed by imaging after MT. If the patient is intolerance with aspirin or clopidogrel, cilostazol / dipyridamole can be used as a substitute.

Standard duration of DAPT

The patients will receive oral (including nasogastric if required) DAPT (aspirin 100 mg and clopidogrel 75 mg per day) for **3 months** within 48 hours after stroke onset if no PH confirmed by imaging after MT. If the patient is intolerance with aspirin or clopidogrel, cilostazol / dipyridamole can be used as a substitute.

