3. PROTOCOL SYNOPSIS

Main Sponsors: 1. Shanghai Hospital 2. TGI, CHINA	Trial Registration: Clinicaltrials.gov (NCT04140110)
Title: Second Enhanced Control of Hypertension and Thrombectomy Stroke Study (ENCHANTED2)	
Study Duration: 4 years	Clinical Phase: III
Objectives: To determine the effectiveness of more intensive blood pressure (BP) lowering target (<120 mmHg) as compared to a higher BP management target (140-180mmHg) on functional outcome in patients who have had successful recanalization with mechanical thrombectomy (MT) for acute ischemic stroke (AIS) due to large vessel occlusion (LVO).	
Number of Planned Participants: 2257 patients to be recruited from 80-100 hospital sites	
Study Design: International, multicentre, prospective, randomised, open, blinded end-point assessed (PROBE) clinical trial, with the main acute treatment trial of different approaches to BP control and two nested substudies evaluating different approaches to secondary prevention, in this high-risk stroke population.	
Inclusion Criteria: 
 1) Age ≥18 years; 2) Diagnosis of AIS with LVO confirmed by brain imaging; 3) To receive MT <24 hours after AIS onset according to local guidelines; 4) Successful recanalization (TICI score ≥2b) after MT; 5) Sustained systolic BP ≥140 mmHg (defined as 2 successive readings <10 mins) within 3 hours after recanalization; 6) Provide written informed consent (or approved surrogate). 	
Exclusion Criteria: Patients will NOT be eligible if there is one or more of the following: 
 1) Unlikely to potentially benefit from therapy (e.g. advanced dementia) or very high likelihood of death within 24 hours post-MT, judged by responsible treating clinician; 2) Other medical illness that interferes with outcome assessments and follow-up (e.g. known significant pre-stroke disability (mRS scores 3-5), advance cancer and renal failure); 3) Definite indication/contraindication to different intensities of BP lowering treatment; 4) Specific contraindications to any of the BP agents to be used (eg, patients who are hypersensitive (allergic) to any of the ingredients); 5) Patients with aortic isthmus stenosis and arteriovenous shunt (exception: patients with haemodynamically inactive dialysis shunt); 6) Women who are lactating; 7) Currently participating in another trial which would interfere with outcome assessments. 	

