Objective: To determine the effectiveness of short duration of DAPT (6 weeks) compared with standard duration (3 months) on recurrence rate within 12 months in patients with AIS due to large artery atherosclerosis (LAA) who receive MT. Randomisation (allocation 1:1 ratio) will be done via the same system as the main study and stratified by site and randomisation of BP intervention. Randomised patients will be allocated to either short duration group of receiving DAPT (aspirin 100 mg and clopidogrel 75 mg per day) for 6 weeks, or standard duration group of receiving DAPT for 3 months. DAPT treatment will be started within 48 hours after randomisation, and maintained by antiplatelet monotherapy (aspirin or clopidogrel) thereafter. Primary outcome is new stroke event (AIS or ICH) over 12 months.

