6.6 Randomisation

After confirmation of eligibility within 3 hours post-MT, patients will be randomised via a central mobile APP-based, password protected randomisation system developed by Taimei, China. This will be done by connecting the study centre (e.g. catheter lab or stroke unit) to the server at Ali Cloud where the patient will be registered and the randomised treatments will be assigned for each particular patient.

The randomisation sequence will use a minimisation algorithm to ensure balance in key prognostic factors. Patients will be stratified according to:

- 1) Site of recruitment
- 2) Time from onset to recanalization (<6 vs ≥6 hours)
- 3) NIHSS score at admission (<17 vs ≥17)

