6.10 Data Collection and Follow-up

Registration, baseline assessment, and randomisation should be achieved over 15 minutes. Doctor/nursing attendance with the randomised patient is likely to be required for 1-2 hours post-randomisation to ensure the titration of BP lowering in the active group, and consistent BP recordings. All patients are followed daily for 1 week, and then 90 days unless death occurs earlier. Key demographic and clinical data will be collected at randomisation. Follow-up data will be collected on 3 occasions: 24 hours, 7 days (or hospital discharge if sooner), and 90 days. The 90 day evaluations will be conducted in-person or by telephone, by a trained staff member at the local site who is blind to the treatment allocation. Brain imaging (CT scan and/or MRI, with any associated diffusion/perfusion and angiogram images) will be conducted according to standardized techniques at baseline, within 24-48 hours (ie next day follow-up scan), and at a later stage in all surviving patients who may deteriorate or for other clinical

reason during follow-up. Brain imaging (CT scan and/or MRI) must be uploaded to the ENCHANTED2 server, either directly from the hospital site (if they have suitable broadband internet) or via the RCC office, to be analyzed centrally for measurement of any ICH or haemorrhagic complications of the ischemic lesion, and for future measurement of areas of infarction, ischemic penumbra, and site of LVO. The LCC will keep a hard copy in an uncompressed DICOM format onto a CD-ROM for monitor site verification (**see Appendix 3**). Trial management is facilitated by an established internet-based system.

All randomised patients will be followed up to 90 days, or death if prior to 90 days. Patients who do not follow the protocol and/or discontinue allocated management should still be followed up to 90 days as their data will be analyzed on the 'intention to treat' principle. **Table 3** illustrates the schedule and nature of the data collection required during the study period. The paper version of the case reports forms (CRFs) will be supplied with the procedure manual, as a reference only, together with a guide to completion of each data element and a definition of terms.

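### The DAPT start window runs from randomisation in the synopsis but from stroke onset in Protocol 11.2.3, and 11.2.3 does not say which post-MT scan must exclude PH before treatment starts

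*Protocol*

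**What the plan says.** The synopsis (Protocol section 3), in its paragraph on the duration of DAPT, says: "DAPT treatment will be started within 48 hours after randomisation". It attaches no imaging condition.

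Protocol 11.2.3 counts from onset three times. The design paragraph has patients allocated to one or other duration "of DAPT within 48 hours after AIS onset". The short-duration and standard-duration descriptions then each use the same sentence, with treatment given "within 48 hours after stroke onset if no PH confirmed by imaging after MT".

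The surrounding timings are:

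- **MT:** the inclusion criterion is "To receive MT <24 hours after AIS onset according to local guidelines".
- **Randomisation (6.6):** "After confirmation of eligibility within 3 hours post-MT, patients will be randomised". For the substudy, "randomisation will be undertaken post-MT at the same time of the main study" (11.2.3).
- **Follow-up scan:** under the Day 1 form in 6.10.5, brain imaging "should be undertaken at 24-48 hours post-MT". Section 6.10 gives "within 24-48 hours (ie next day follow-up scan". Appendix 3 asks for a scan at 24 hours in all patients without saying from when. Further imaging is listed for Day 7, or discharge if earlier.

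The SAP gives no DAPT start window.

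**The concern.** Two operative parts of the protocol give different start rules for the same treatment. They differ in time origin and in whether imaging must first exclude parenchymal haemorrhage (PH). Nothing in either document says which prevails.

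A start that falls between the two deadlines would be adherent under one text and a deviation under the other. Sites could also start DAPT with different information about bleeding, depending on which text they follow and which scan they take as sufficient. SAP 3.9 presents the substudies as feasibility work on recruitment, safety and adherence, with ICH among the main outcomes. Adherence to a start rule cannot be scored while there are two rules.

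**Working it through.** No calculated figure in the plan depends on the start window, so there is no stated number to reproduce. The check is a timeline in hours from stroke onset.

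**Inputs**

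- m = onset to MT: above 0 and below 24 (inclusion criterion). MT is treated as a single time point.
- r = MT to randomisation: 0 to 3 (section 6.6), the same for main study and substudy (11.2.3).
- s = MT to scheduled follow-up scan: 24 to 48 (6.10.5).

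**Gap between the two deadlines**

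- Deadline in 11.2.3: 48.
- Deadline in the synopsis: m + r + 48.
- Difference: m + r. The upper bound is 24 + 3 = 27 h, which puts the synopsis deadline at up to 75 h from onset against 48 h in 11.2.3.

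Example: MT at 23 h and randomisation at 25 h give deadlines of 48 h (11.2.3) and 25 + 48 = 73 h (synopsis). A start at 60 h meets the synopsis and breaches 11.2.3.

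**Scheduled scan against the onset deadline**

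The scan takes place at m + s. It comes after the onset window has closed when m + s > 48, that is, when s > 48 - m.

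| MT at (m, h) | Scan window from onset (h) | Latest scan still inside 48 h from onset (h post-MT) | Time left at earliest / latest scan (h) | Share of 24-48 h scan window inside the limit |
|---|---|---|---|---|
| 3 | 27-51 | 45 | +21 / -3 | 88% |
| 6 | 30-54 | 42 | +18 / -6 | 75% |
| 12 | 36-60 | 36 | +12 / -12 | 50% |
| 18 | 42-66 | 30 | +6 / -18 | 25% |
| 23 | 47-71 | 25 | +1 / -23 | 4% |
| 24 (limit) | 48-72 | 24 | 0 / -24 | 0% |

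The last column is (48 - m - 24)/24. It is a share of the permitted scan window, not a proportion of patients.

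A scan at s = 48 falls at m + 48, which is past 48 for every m above 0. The timing of the scan therefore matters as well as the timing of MT.

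**Scheduled scan against the synopsis deadline**

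The synopsis deadline, m + r + 48, is never earlier than the latest scheduled scan, m + 48. The timing conflict with the scan therefore arises only under the onset clock. That is a statement about arithmetic, not about which clock is clinically appropriate.

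**The case against.** The strongest reply is that the two rules are nested. Onset precedes randomisation, so any start after randomisation and within 48 h of onset is also within 48 h of randomisation. A site that follows 11.2.3 in full breaches neither text, and the only outlier is one sentence in the synopsis. The nesting is correct. It does not help a site that follows the synopsis, and no order of precedence is stated.

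Three stronger readings are tempting, and the documents do not support them.

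- *The onset window always closes before the scan it needs.* Section 11.2.3 asks only for imaging after MT and names no scan. An earlier unscheduled scan could meet the condition; 6.10 and Appendix 3 provide for extra scans on deterioration, and Appendix 3 also when haemorrhage is suspected. If the 24 hours in Appendix 3 run from MT, that scan falls before 48 h from onset for any MT before 24 h, though with about 1 h to spare for MT at 23 h.
- *Only patients treated late are affected.* With MT at 3 h and a scan at 48 h post-MT, the scan is at 51 h from onset. Late MT makes the overlap smaller, but early MT does not remove the problem.
- *The comparison of the two durations is biased.* Both arms have the same start wording and imaging condition, and allocation is minimised by site. Differences between sites in reading the rule should be roughly balanced between arms, and no mechanism for bias is apparent.

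It is also fair that 27 h is a worst case, that this is a pilot substudy, and that neither SAP 3.9 nor the per-protocol set in SAP 3.2 uses a DAPT start time. These points limit the severity but leave the contradiction in place.

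**Conclusion.** The start rule is contradictory as written: the synopsis and 11.2.3 differ in time origin and in imaging condition. The deadlines differ by the onset-to-randomisation time, at most about 27 h. This bound assumes MT is a single time point before 24 h and randomisation follows within 3 h; the bound would be larger if the 24 h refers to the start of a long procedure. The documents give no distribution of onset-to-MT or scan times, so the typical gap and the number of patients affected are unknown.

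The scan finding is narrower. Section 11.2.3 leaves the qualifying scan unnamed, and the earliest one scheduled for everyone can fall after the onset window has closed. Whether it does depends on when MT and the scan take place and on whether an earlier scan was done.

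The consequence is for how adherence is scored and what bleeding information is available at the start of DAPT, both within the substudy's stated purposes. No bias between arms is shown, and the main BP comparison is not in question. It should be corrected, but it is not critical.

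**What to change.** 1. Reconcile the synopsis and 11.2.3 to one time origin for the DAPT start, and state the same imaging condition in both places.
2. State in 11.2.3 which post-MT scan satisfies the condition.
3. Align that with the scan timing in 6.10, 6.10.5 and Appendix 3, and give the time origin of the 24 hours in Appendix 3.

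The clinical leads must decide which start rule and which scan apply; this review takes no position on that. The cost is amendment wording and a notice to sites.
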